## **6. Study Design**

This is a multi-center post-market observational study. It is anticipated that 100 or more eligible centers will participate. There is no upper limit for the number of enrolled subjects. Eligible candidates will be approached to ascertain interest in study participation at their initial follow up visit. If a subject has had CorMatrix ECM used in their surgery they will be asked to allow their physician to use their medical information from the surgical procedure and the current visit. All elements of the approved informed consent will be provided verbally and the process will be documented in the subject study binder by the research staff. A copy of the consent will be provided to the participant. This study includes a one-time visit at the initial post-operative visit.

## **7. Study Population**

The study population will consist of any subject who has received CorMatrix ECM for pericardial reconstruction. Subjects will be considered enrolled into the study once they have given permission for their medical information to be collected. Before any subject can be enrolled, the IRB for the specific institution must approve the protocol, the informed consent form to be used at that site and a Waiver of Documentation of Consent.

## **8. Study Methods**

Study procedures are standardized to the extent possible and all study-related data will be captured on a standardized Case Report Form. A copy of the Case Report Form is provided in Appendix A.

## 9. Study Procedures

Patients returning for a post-operative visit following a surgical procedure with pericardial reconstruction with CorMatrix ECM will have the following information collected and documented:

- Documentation of the consent process and verbal approval by subject
- Demographic information
- Pre-operative risk factors
- Surgical procedure
- Blood transfusion information, if applicable
- Chest tube placement information
- Surgical complications
- Use of anticoagulation medication
- Cardiac related procedures since surgical procedure
- Device related adverse events

All study-related data will be captured on a standardized Case Report Form. A copy of the Case Report Forms is provided in Appendix A. Case report forms will be sent to CorMatrix via email or mail. Stamped, self-addressed envelopes will be provided.

[name]  
CorMatrix Cardiovascular, Inc.  
[name]  
[name]  
[contact] Direct Office  
[contact]

## 10. Adverse Event Reporting

### 10.1 Definitions

#### **Adverse Event (AE)**

An adverse event (“AE”) will be defined as any undesirable clinical occurrence in a subject whether it is considered to be device related or not, that includes a clinical sign, symptom, or condition and/or an observation of an unintended technical performance or performance outcome of the device. Causality is defined as not-related, possibly-related, and probably-related to the device. This post market clinical study will collect only events that relate to the use of the CorMatrix ECM as well as any pericardial reconstruction clinical findings.

#### **Serious Adverse Event (SAE)**

A serious adverse event (“SAE”) will be defined as an event that: 1) threatens life, 2) results in permanent impairment of a body function or permanent damage to a body

structure, 3) necessitates medical or surgical intervention to preclude such impairment, 4) requires or prolongs hospitalization, or 5) is fatal (death).

### **Adverse Device Event**

An Adverse Device Event will be defined as a clinical sign, symptom, or condition that is causally related to the device procedure, the presence of the device, or the performance of the device. Due to the temporal proximity of the AE to product administration, there is a reasonable possibility that the product may have caused the AE or may have contributed to the severity or duration of an event caused by other means.

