effectiveness endpoints, the rate of treated or sustained episodes of new onset post-operative atrial fibrillation (defined as a single episode lasting 15 minutes or more), and the rate of treated episodes of new onset post-operative atrial fibrillation, the results were also similar between the two groups (36.8% versus 35.0% and 27.4% versus 22.1%, respectively, for the ECM group compared with the control group).

The composite primary endpoint event rates for the ECM and control group were 3.9% and 3.7%, respectively. Using the protocol specified non-inferiority margin, 7.5%, the ECM was shown to be non-inferior to control for the primary safety endpoint ( $p < 0.001$ ). Therefore, the primary safety endpoint for the study was achieved. The composite secondary safety event rate was similar for the two groups (5.8% for the ECM group compared with 3.9% for the control group) demonstrating no significant increase in the rate of bypass graft failure in the ECM group compared with the control group.

Although the study failed to demonstrate a reduction in the incidence of new onset post-operative atrial fibrillation, the study demonstrated that the CorMatrix ECM for Pericardial Closure continues to be safe for its intended use, with no significant increase in the rate of bypass graft failure or cardiac tamponade compared with no pericardial closure.

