### Endpoint

The endpoint is defined as the proportion of subjects with device related adverse events.

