## ***10.3 Possible Adverse Events***

Potential risks are the same as those associated with any thoracic surgery procedure, including bleeding, MI, stroke, death, and scarring from the incision. There is also a risk of infection and/or wound healing complications, but an increase in these

complications over standard thoracic surgery has not been observed in other pericardial closure/reconstruction. This study will capture events reported at the first (initial) postoperative follow up as reported by the PI and/or subject and from a review of medical records.

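### The Adverse Device Event definition offers only timing as a ground for attributing an event to the device, and in this design timing cannot separate device events from surgical ones

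*Protocol*

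**What the plan says.** Protocol section 5 (Endpoint) names a single endpoint: "The endpoint is defined as the proportion of subjects with device related adverse events". Two parts of section 10.1 bear on what counts as device related.

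- **Adverse Event** sets a scale: "Causality is defined as not-related, possibly-related, and probably-related to the device". It gives no criteria for the three levels and does not say which of them count towards the endpoint. It also limits collection to events related to use of the ECM, plus clinical findings on the pericardial reconstruction.
- **Adverse Device Event** has two sentences. The first requires that the event be "causally related to the device procedure, the presence of the device, or the performance of the device". The second supplies the reasoning: "Due to the temporal proximity of the AE to product administration, there is a reasonable possibility that the product may have caused the AE". It then adds that the product "may have contributed to the severity or duration of an event caused by other means".

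The detail list in section 10.2 asks for relationship to the procedure/surgery on the same three levels. Relationship to the device is not in that list, which is stated not to be exhaustive.

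On observation, section 6 says: "This study includes a one-time visit at the initial post-operative visit". No day window is given. On expected events, section 10.3 says: "Potential risks are the same as those associated with any thoracic surgery procedure, including bleeding, MI, stroke, death, and scarring from the incision".

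**The concern.** Closeness in time helps attribution when exposure to the product can be separated in time from the other likely causes. Here it cannot. The patch goes in during the operation, every subject receives it, and follow-up ends at the first post-operative visit. The period in which a device event could be seen is the same period in which complications of the operation are expected.

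The first sentence of the definition does not supply what timing lacks. It demands causation without saying how to judge it, and it admits events caused by the device procedure, which in practice is part of the cardiac operation. The contribution clause widens the definition further, to events with a known other cause.

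At stake is the meaning of the one endpoint. Section 6 expects 100 or more centres, and no event adjudication is described, whereas the randomised trial in section 4.1 had a blinded Clinical Events Committee. Section 11 plans comparisons with literature and similar studies, which need a stable case definition. The classification is made by investigators at data capture, so an analysis plan could not readily repair it afterwards.

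**Working it through.** The study states no sample size, margin or expected rate, so there is no planned figure to reproduce. The check is a comparison of texts, followed by an illustration of scale.

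**Step 1: does timing discriminate?**

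| Feature | Where | Consequence |
|---|---|---|
| Device implanted during surgery | sections 1 and 3 | time since device = time since operation |
| Observation ends at the initial post-operative visit | sections 6 and 10.3 | all events fall in that one interval |
| All subjects received ECM | section 7 | no internal comparator |
| Risks are those of thoracic surgery | section 10.3 | event types overlap |

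A criterion that takes the same value for device events and surgical events cannot tell them apart.

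**Step 2: do other provisions separate them?**

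| Provision | What is related to what |
|---|---|
| 10.1 Adverse Event | event to device, three levels, no criteria |
| 10.1 Adverse Device Event | event to device procedure, presence or performance; includes contribution to events with another cause |
| 10.2 detail list | event to procedure/surgery, three levels |

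Three places use different referents. None of them calls for both a device grade and a surgery grade on the same event.

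**Step 3: scale, as illustration only.** Inputs are the five pairs of rates in section 4.1; for treated atrial fibrillation (AF), for example, the protocol gives "27.4% versus 22.1%, respectively, for the ECM group compared with the control group". Excess = ECM rate − control rate. Background share = control rate / ECM rate.

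| Outcome | ECM | Control | Excess (points) | Background share |
|---|---|---|---|---|
| Primary AF | 38.3% | 35.9% | 2.4 | 35.9/38.3 = 94% |
| Treated or sustained AF | 36.8% | 35.0% | 1.8 | 35.0/36.8 = 95% |
| Treated AF | 27.4% | 22.1% | 5.3 | 22.1/27.4 = 81% |
| Composite primary safety | 3.9% | 3.7% | 0.2 | 3.7/3.9 = 95% |
| Composite secondary safety | 5.8% | 3.9% | 1.9 | 3.9/5.8 = 67% |

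The sentence giving 35.9% is cut off in the text at hand; I read it as the control rate. If every event of one of these kinds in an ECM cohort were attributed to the device on timing, 67% to 95% of the count would be events also expected without it. These are ratios of point estimates and carry sampling error.

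**The case against.** A reader might infer that nearly every post-operative complication meets the device criterion, so that the endpoint becomes the background complication rate. The protocol does not support that. The first sentence of the definition still requires a causal relation, and the scale in section 10.1 includes not-related. The synopsis and section 9 list surgical complications separately from device related adverse events, so a routine bleed has its own item. Section 10.2 has the sponsor ask for underlying cause and coexisting disease. The visit need not be early either, since no window is stated.

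A reader might also infer that some sites would report the full background rate and others almost none, leaving a pooled figure that reflects site habit. Nothing in the protocol shows how sites would behave. Inconsistent classification is a risk, not a finding.

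The illustration has limits too. The randomised trial took isolated first-time CABG patients without prior atrial fibrillation and used a core laboratory for arrhythmia. This study takes any recipient of the ECM for pericardial reconstruction and describes no rhythm monitoring. The size also depends on the outcome chosen: 27.4% for treated atrial fibrillation, 3.9% for the safety composite.

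Three further points carry some weight. The protocol does not say that the Adverse Device Event definition governs the endpoint. The Case Report Form is a separate document and may hold relatedness items. An inclusive definition is defensible for descriptive post-market surveillance whose data will not support a marketing claim or labelling change.

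These points narrow the concern but do not remove it. No criterion other than timing is offered for judging causation, the causality levels are undefined, and the referents differ between places.

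**Conclusion.** The point holds in limited form. Ordinary surgical complications can, but need not, be counted as device related, and the sole endpoint cannot reliably separate the two. The cause is a definition whose only stated ground for attribution does not discriminate in this design, which also admits procedure-related events and events with another cause, alongside a detail list that grades relation to surgery rather than to the device.

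The size of any bias cannot be derived from the protocol. The background shares of 67% to 95% show only that background events can dominate a timing-based count in a similar setting.

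The conclusion assumes that investigators use the Adverse Device Event definition when judging events for the endpoint, and that the Case Report Form does not already require separate device and surgery grades with a stated basis. It is worth correcting, because the endpoint depends on it and the change is small.

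**What to change.** 1. In section 10.1, Adverse Device Event, replace the sentence on temporal proximity with a statement that timing after implantation does not by itself establish device relatedness.
2. In the same definition, separate relation to the device (its presence or performance) from relation to the surgical procedure. If the device procedure stays within the device criterion, surgical complications can still qualify.
3. Align both definitions in section 10.1 with section 10.2, so that each recorded event is graded twice on the existing three-level scale, once for the device and once for the procedure/surgery, with the basis for the device grade noted.
4. Keep recording, as possibly-related, events in which a device contribution cannot be excluded. A device-specific sign should not be a condition for recording: section 10.1 limits collection to events related to the ECM, so such a condition could lose possible device events altogether.
5. Report the endpoint twice: for probably-related events, and for possibly- or probably-related events together.

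The cost is an amended definition, one more item on the form and one more table row. The probably-related figure may omit some true device contributions; the broader figure still shows them.

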## ***10.2 Assessing and Recording Adverse Events***

Each AE recorded must be documented on the Case Report Form. All serious and device related events must be reported immediately to CorMatrix via telephone or email within 24 hours of the Investigator becoming aware of the event. The case report form will be submitted to CorMatrix. The site will be contacted by CorMatrix for additional information including, but not limited to:

- Description of the event and underlying cause (diagnosis), coexisting disease, or other.
- Date of onset and date of resolution. If the event is present at the single post-operative visit it will be marked as unresolved.
- Intensity of the event: mild, moderate, or severe.
- Frequency of the event: single episode, intermittent, or continuous.
- Action taken: none, medication, procedure, medication and procedure, or other.
- Relationship to the procedure/surgery: not-related, possibly-related, or probably-related.

The Investigator must ensure that the details of the event are documented in the medical notes including full details of the outcome, in addition to recording the event on the appropriate case report form.

Serious adverse events and/or device related events contact information at CorMatrix:

[name]  
Quality Systems Manager, CorMatrix  
[contact]  
[[contact]](mailto:[contact])

## ***10.3 Possible Adverse Events***

Potential risks are the same as those associated with any thoracic surgery procedure, including bleeding, MI, stroke, death, and scarring from the incision. There is also a risk of infection and/or wound healing complications, but an increase in these

complications over standard thoracic surgery has not been observed in other pericardial closure/reconstruction. This study will capture events reported at the first (initial) postoperative follow up as reported by the PI and/or subject and from a review of medical records.

## **11. Data Analysis**

Since this is a post-market study, analyses will consist of tabulated data and descriptive statistics. Subject data listings and tabular and graphical presentations of the summary and statistical results will be provided. Additional quantitative and qualitative comparisons will be made to contemporary literature and similar studies

## **12. Ethical Considerations**

### ***12.1 Code of Conduct***

The Investigator will ensure that the clinical study is conducted in accordance with good clinical practice and all regulatory and institutional requirements, including those for subject privacy, informed consent, Institutional Review Board or Ethics Committee approval, and record retention. (Appendix D: Investigator Qualifications and Responsibilities)

### ***12.2 Ethics Committee / Institutional Review Board Approval and Oversight***

The Investigator must obtain appropriate Ethics Committee (“EC”) or Institutional Review Board (“IRB”) approval before the study can be initiated. A copy of the written approval from the EC/IRB and a copy of the approved Informed Consent Form (approved Waiver of Documentation of Consent, if applicable) should be sent to CorMatrix.

Appropriate study progress reports will be prepared for the EC/IRB by the Principal Investigator. Any changes to the protocol must be discussed and approved by CorMatrix in writing unless the change is made to assure the safety of the subject. In the non-emergent setting, after agreement on the changes has been reached, an amendment to the protocol will be provided by CorMatrix for submission to the EC/IRB for review and approval prior to initiation of the change. Any change made emergently must be documented in the subject's medical record. The Investigator must immediately forward to the EC/IRB any written safety reports or updates from CorMatrix.

### ***12.3 Informed Consent Documentation and Subject Confidentiality***

The investigator will be responsible for submitting the clinical study protocol and Informed Consent/Waiver of Documentation of Consent to their EC/IRB or centralized EC/IRB. The Informed Consent/Waiver of Documentation of Consent and protocol must be approved by the local/centralized EC/IRB before the study is initiated and subjects enrolled. Prior to obtaining any study specific information approved informed consent will be reviewed with the subject and the subject must provide verbal approval. Documentation of the consent process must be completed by the research personnel. The

investigator shall provide a copy of the Informed Consent to the subject. Completed documentation of the consent process will be available for auditing by CorMatrix or their representative, as applicable.

CorMatrix will maintain the confidentiality of the identity of subjects enrolled in the study and the information contained in their study records. CorMatrix will also instruct the study investigators in the importance of maintaining the confidentiality of study records. Any publication of any data collected as part of this trial will only use de-identified data, so that identification of any individual subject will not be possible. The records will be made available as required for review by the FDA, or other applicable regulatory agency and a reviewing EC/IRB; however to the extent possible, the subject's identity will not be disclosed. The Case Report Forms will use a subject identification number, with the patient name and address NOT appearing anywhere on the study form to be submitted to the sponsor (Appendix C: Sponsor's Commitments).

## **Appendix A**

### **Case Report Form**

To be provided as a separate document

## **Appendix B**

### **Instructions for Use**

To be provided as a separate document

## **Appendix C**

### **Sponsor Commitments**

#### **SPONSOR'S COMMITMENTS**

CorMatrix is committed to:

1. Complying with the Declaration of Helsinki and all applicable health authority regulations governing the conduct of clinical research studies.
2. Protecting the rights, health, safety and welfare of study subjects.
3. Informing the clinical investigators of any new information about the study which may affect the health, safety, or welfare of the subjects, or may influence their decision to continue participation in the study.
4. Providing the clinical investigators with the study protocol and Case Report Form on which to document the study evaluation variables for each subject entered into the study.
5. Providing the clinical investigators and study staff training on the protocol and completion of the Case Report Form.
6. Providing the statistical analysis and study report writing resources necessary to complete reporting of the study results.
7. Certifying that EC/IRB approval of the protocol and Investigators Agreement will be completed prior to treatment at a clinical site.

## **Appendix D**

### **Investigator Qualifications and Responsibilities**

#### **INVESTIGATOR QUALIFICATIONS AND RESPONSIBILITIES**

Each investigator must be a licensed physician who has received training for using the CorMatrix ECM for the reconstruction and repair of the pericardium. The investigators have the following responsibilities:

##### **1. Subject Selection**

The investigator is responsible for assuring that all subjects entering the study are eligible to participate.

##### **2. Informed Consent**

The investigator is responsible for fully reviewing the nature of the study. The investigator is responsible for documenting the Informed Consent process in compliance with applicable regulations for each patient, prior to enrollment in the trial. A copy of the Informed Consent Form and documentation of the consent process will be maintained in the patient's medical record.

##### **3. Ethics Committee (EC)/Institutional Review Board (IRB) Approval**

The investigator must obtain approval for his participation in this protocol from an EC/IRB prior to entering any patients in the study. The Informed Consent document and Waiver of Documentation of Consent to be used will also be submitted by the Investigator to the EC/IRB for approval prior to initiation of the study. Assurance that the EC/IRB approval of the study protocol and Informed Consent/Waiver of Documentation of Consent has been obtained will be provided to the Sponsor prior to initiation of the study.

##### **4. Subject Evaluation and Data Reporting**

The investigator is responsible for performing the patient evaluations as described in the study protocol. All information generated by the patient evaluation will be recorded on the Subject Case Report Form provided by the Sponsor. The Case Report Form will be filled out in black ink. Any corrections will be made by lining out with a single line, providing the date of corrections and initials of person making the correction. Correction fluid will not be used. The person completing the form will date and initial each form upon its completion and will send the form via mail, email or fax to CorMatrix. Copies of all Case Report Forms will be retained in the Investigator's office.

